After IRB approval and written informed consents, participating individuals will be categorized to novice or expert groups depending on previously described criteria/years of clinical experience. From these groups, they will be randomized via blindly selecting pieces of paper marked MVG or 2VE. There will be two boxes, one for novices with 16 pieces of paper (8 marked MVG/8 marked 2VE), and one for experts with 16 pieces of paper (8 marked MVG/8 marked 2VE.) Whichever option is selected (MVG or 2VE), the participant will begin with this technique and then switch to the alternative.

ev,The participants will then be guided to the OR simulator where the SimMan Essential patient stimulator (Laerdal Medical Wappingers Falls, NY) (manikin) will be placed supine on aa hospital bed. After this, mask holding technique with MVG device and without (2VE) will be demonstrated by investigators, who will then reviewparticipants' subsequent techniques to ensure consistency throughout the experiment. The parameters for the anesthesia workstation/OR simulator will be checked and confirmed by one or more members of the research team for every participant before the baseline information of participants' demographics and level of experience is recorded. They will be instructed to maintain as tight a seal between the mask/manikin face as possible, that the "patient" only requires mask ventilation during the entire scenario, and that there is no need to perform

additional emergency maneuvers such as chest compressions. The ventilation mask will be connected to an air flow supply via the anesthesia machine ventilator.

Participants will then don their desired sized gloves and perform MVG or 2VE for 30 breaths (approximately 3 minutes) in accordance with the techniques demonstrated previously as an investigator in the room records tidal volumes achieved for each breath onto a data sheet and a separate camera in the OR simulator also simultaneously records the encounter. Tidal volumes will not be recorded until a proper seal is established so participants are aware of what a mask leak feels like. After providing mask ventilation with MVG or 2VE for 30 total breaths, participants are given a 5-minute rest period during which they were to complete the given NASA-TLX and SOFI instruments described above.

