After completion of the surveys and the 5-minute rest period, participants were instructed to provide mask ventilation for another 30 machine-delivered breaths utilizing the alternative technique that they had not performed in the previous mask ventilation period. After this period of providing ventilation, participants were again asked to complete another set of NASA-TLX and SOFI instruments in respect to the mask ventilation technique they had just used.

As the final component of the experiment, participants will have their dominant hand measured for hand span, palm circumference, and max grip force produced. Participants will be instructed to spread their fingers on their dominant hand as wide as possible, after which a measuring tape will be used to record the distance from the distal tip of the fifth digit to the distal tip of the first digit in centimeters. Subsequently, participants will be instructed to bring their fingers together, while keeping their first digit fully abducted. From this position, the measuring tape will be used to record the circumference of the widest portion of the palm in centimeters. After these measurements, investigators will demonstrate for the participants, how to grip the dynamometer while having the dorsum of their dominant hand resting against another table from a sitting position. Participants will be given 3 attempts to grip the device as forcefully as possible, from which the average force (kg) will be used as a final number.

All experimental runs will be conducted in the OR simulator at the Center for Patient Safety (CPS) Miller School of Medicine downtown campus of the University of Miami. The OR simulator consists of a SimMan Essential human patient simulator (Laerdal Medical Wappingers Falls, NY) an anesthesia workstation (Datex-Phmeda, GE Healthcare, Little Shalfont, UK,) and an ASL 5000 artificial lung (IngMar Medical, Active Servo Lung, Pittsburgh, PA.)

From the control room, an adjacent room with computers and one-way mirror view of the OR simulator, a CPS technician and another investigator operating the anesthesia workstation will input the following experimental parameters: pressurecontrolled ventilation (PCV) ventilator rate (Rate) of 10 breaths/min, peak inspiratory pressure (PIP) of 37 cm H₂O, Trachea (artificial lung) resistance of 175 cm H₂O/L/sec, compliance of 50

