mL/cm H₂O, and the right manikin lung resistance set to 100 cm H₂O/L/sec while the contralateral lung is set to 0 cm H₂O/L/sec. These parameters were designed to mimic the feeling of providing 2VE to difficult patients (obese patient, short neck, obstructive sleep apnea, etc...) while maintaining a tidal volume (TV) of approximately 500 mL \pm 5 mLs. The height of the SimMan Essential Patients Stimulator (manikin) will be adjusted for each participant so that the top edge of the table is flush with the participants' iliac crests. An investigator with a timer will stand approximately 6 feet away from the participants with clear view of the monitors and participants' hands and give out instructions accordingly.

..

Measurements

Baseline information including age, gender and years of experience will be recorded.

Primary outcome: **the difference in the average tidal volume achieved per breath** between the two techniques (MVG and 2VE) in the two groups (novice and expert) as recorded by the anesthesia ventilator over the two 30 breath mask ventilation periods.

Secondary outcomes: Hand fatigue and **difficulty perception**. All participants (both novice and expert groups) will be asked to rate the difficulty of each of the techniques (MVG and 2VE) and express their level of fatigue appreciated by filling out NASA-TLX and SOFI instruments after providing ventilation with each technique.

Exploratory outcome:

Hand fatigue and efficacy of MVG compared to 2VE in regards to participants' hand sizes/grip strength. All participants will have their hand span, palm circumference, and maximum grip force of their dominant hand recorded. This data will be analyzed alongside each participant's answers to the previously described NASA-TLX, SOFI instruments, and gross average tidal volume for each period of ventilation with both techniques.

7) Statistical Analysis

The required sample size for this study was calculated with an online power and sample size calculator for general linear multivariate models (GLIMMMPSE v2.1.0) The parameters used for this study is in JavaScript Object Notation (i.e., JSON) file, which can be uploaded into GLIMMMPSE website and reviewed (URL for GLIMMMPSE program)

A data collection sheet will be used and completed for each included subject. Descriptive statistics will be used for demographic characteristics.

T-paired test model will be used for comparison of the tidal volumes between two groups (MVG and 2VE groups)

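### The only described capture route for the primary tidal volumes is live handwriting by an investigator who can see the technique, with no source of record, masking or check stated

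*Combined protocol and SAP*

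**What the plan says.** Section 6 (Procedures Involved) of the combined protocol and SAP describes two runs of 30 machine-delivered breaths per participant, one with each technique. In each run "an investigator in the room records tidal volumes achieved for each breath onto a data sheet". Filming takes place as well, in that "a separate camera in the OR simulator also simultaneously records the encounter". On when recording begins, it says "Tidal volumes will not be recorded until a proper seal is established". It gives no criterion for a proper seal and names no one to judge it.

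Further on, section 6 lists the equipment, which includes an anesthesia workstation and "an ASL 5000 artificial lung". No data capture from the artificial lung is described. An investigator with a timer stands about 6 feet away with a "clear view of the monitors and participants' hands and give out instructions accordingly". The plan does not say whether this is the person who writes down the values.

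Under Measurements in section 6, the primary outcome is the between-technique difference in average tidal volume per breath, "as recorded by the anesthesia ventilator over the two 30 breath mask ventilation periods". Section 2 (Objectives) measures objective fatigue by how tidal volume changes from breath to breath over the runs. Section 7 provides one data collection sheet per subject, and section 9 has the data moved to a spreadsheet.

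The plan does not say which record (sheet, ventilator or video) is used for analysis, what happens if they disagree or a breath is missed, whether any recorder or analyst is masked, or whether either manual step is verified.

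**The concern.** The grip is a visible add-on to the mask, so anyone in the room knows which technique is in use. The values for the primary outcome, and for the objective fatigue measure, reach the dataset through that person's handwriting and then through a spreadsheet transfer. The outcome definition points to the ventilator, but no step describes taking values from the ventilator other than by hand.

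Two things are at stake. First, if errors in reading or writing lean towards one technique, the primary comparison is biased, and recruiting more participants does not help. Second, the fatigue measure depends on breath order, and a live transcript made every few seconds can lose that order without leaving a trace.

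**Working it through.** **Inputs**
- Breaths per run: 30, stated to take about 3 minutes (section 6).
- Ventilator rate: 10 breaths/min (section 6).
- Runs per participant: 2 (section 6).
- Participants: 16 novice and 16 expert randomization slips, 16 + 16 = 32 (section 6).
- Size of reading error: not in the documents. The values below are assumptions, shown as a range.

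**The plan's own figure.** 30 / 10 = 3.0 min per run, which agrees with the stated 3 minutes.

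**Recording load.** 60 s / 10 = 6 s per value. 30 × 2 = 60 values per participant. 60 × 32 = 1,920 values in all.

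**Random error.** Suppose each written value carries an independent error with SD e. A participant's difference between two 30-breath means then gains an SD of e × √(2/30), and the mean difference over 32 participants gains a standard error of that amount divided by √32.

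| Assumed e (mL) | SD added to a participant's difference (mL) | SE added to the mean difference, n = 32 (mL) |
|---|---|---|
| 5 | 1.29 | 0.23 |
| 10 | 2.58 | 0.46 |
| 25 | 6.45 | 1.14 |
| 50 | 12.91 | 2.28 |

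Random slips therefore largely average out.

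**Differential error.** If values under one technique are shifted by b on average, the mean difference is biased by b, whatever the sample size. If a share p of one technique's breaths is misread by m in the same direction, the bias is p × m: 0.10 × 50 = 5 mL, 0.10 × 100 = 10 mL, 0.05 × 100 = 5 mL. These are illustrations. The documents give no evidence that such errors would occur, and no size for them.

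**Breath order.** Permuting the 30 breath numbers leaves the run mean unchanged but changes the trend over the run. Misnumbering therefore falls on the fatigue measure and not on the mean. How much it matters depends on how many breaths are affected, which is unknown.

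**Start of recording.** The rule excludes breaths before a proper seal, in a study whose outcome reflects the quality of the seal. Moving breath 1 changes which 30 breaths are averaged. That choice involves judgement, whereas copying a number from a display involves little.

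**Video reading time.** 32 participants × 2 runs × 3 min = 192 min.

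**The case against.** The strongest reply is that the value is a number produced by a machine. Reading it leaves little room for opinion, and the table above shows that ordinary slips do almost nothing to the mean difference. Only a consistent lean towards one technique would matter, and nothing in the documents points to one. This stands, and it limits the point to a cheap improvement.

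Several stronger readings are tempting, and the documents do not support them.
- A reader might infer that instrument and camera records of every breath already exist, so that the handwriting is plainly avoidable. The plan does not say that the ventilator or the artificial lung stores or exports per-breath values. It does not say that the ventilator display is in the camera's view.
- A reader might take the hand sheet to be the designated data source. It is the only capture step described, but the outcome definition names the ventilator. The gap is that no source of record is chosen.
- A reader might suppose that missed breaths would be filled in by someone who knows the technique. No such step appears. They could be left blank or checked against the recording.
- A reader might scale the bias against 75 mL of headroom, taking 2VE to reach 85% of 500 mL. The 85% is a background figure for two-handed ventilation in cited work, and nothing says that 2VE will reach it in this set-up.

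It is also fair to object that an electronic record does not by itself remove observer influence, because someone must still decide which breath is breath 1. That stands, and the fix has to cover it.

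**Conclusion.** The point holds as a low-cost improvement to data capture. One unmasked, unverified handwritten transcript is the only described route for the primary outcome and for the objective fatigue measure, and the plan leaves the source of record open. Random copying error is negligible for the mean difference (an added standard error of about 0.2 to 2.3 mL, for an assumed SD of 5 to 50 mL and 32 participants). Differential error would pass into the mean difference one for one, and misnumbered breaths would distort the breath-by-breath trend. Neither size can be derived from the documents. The undefined, unmasked judgement of when recording starts is a larger route for observer influence than the copying itself. Sample size, power and alpha are not affected.

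The conclusion rests on the recorder being able to see the technique, which follows from being in the room with a visible device. The preferred remedy also assumes that per-breath values can be exported, which the plan does not state. The fallback does not need that.

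**What to change.** In section 6:
- Name the ventilator's own per-breath record as the source for the primary outcome, if it can be exported, and keep the hand sheet as backup.
- If it cannot be exported, frame the existing camera on the ventilator display. Have a current team member transcribe the values, or check the sheet, from that display-only view. Label the clips by participant code and run number, not by technique. Because starting technique is randomized, run number does not reveal it.
- Identify breath 1 from that record by a rule written in advance and identical for both techniques, in place of an unmasked judgement of seal.
- State how missed breaths and disagreements between sources are handled.

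If the artificial lung's volume is used instead, amend the primary outcome definition under Measurements to match, since it now names the ventilator.

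The cost is a few sentences in section 6, plus either file handling or about 192 minutes of footage to read, with pauses extra. No participant time or new staff is needed. Turning the camera to the display may give up the wider view of the encounter, for which the plan states no use.

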Title: Improvement of Manual Ventilation Efficacy with Ventilation Grip Device: a manikin study

Document Date: 21 April 2022

Study NCT Number: NCT05059366

1) **Protocol Title**

Improvement of Manual Ventilation Efficacy with Ventilation Grip Device: a manikin study.

Principal Investigator: [name]

Setting: Center for Patient Safety, University of Miami Miller School of Medicine

2) **Objectives***

PRIMARY OBJECTIVES:

Primary aim: Our primary goal is to assess the efficacy of the Mask Ventilation Grip (MVG) device via comparison of the average tidal volumes achieved during respiration using the MVG device compared to the standard two-handed V-E technique(2VE),by measuring the average tidal volume(s) achieved as well as changes in the obtained tidal volumes over a duration of two three-minute cycle in both experienced (expert) and inexperienced (novice) clinicians

Primary hypothesis: Specifically, we hypothesize that use of the MVG device when providing two-handed mask ventilation will improve the average tidal volumes achieved compared to the standard 2VE technique in both expert and novice groups in a manikin simulation setting with novices appreciating a greater increase in average tidal volume than experts

SECONDARY OBJECTIVES:

Secondary aim 2: Our second aim is to investigate the level of perceived difficulty and fatigue experienced while using of the MVG device versus the standard 2VE technique. in both expert and novice groups

Secondary hypothesis: Providing mask ventilation to a manikin is easier (subjective perception of difficulty) when using the MVG device compared to the standard 2VE technique in both groups, with the novice group demonstrating a greater ease to ventilate. Hand-fatigue is reduced by using the ventilation grip device compared to the standard 2VE technique in both expert and novice groups with the novice group appreciating a greater reduction in fatigue with the MVG compared to 2VE than the expert group.

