Subjectively, participants will fill out NASA-TLX (NASA Task Load Index) and SOFI (Swedish Occupational Fatigue Inventory) questionnaires. "The NASA task load index (NASA TLX) is a tool for measuring and conducting a subjective mental workload (MWL) assessment. It allows you to determine the MWL of a participant while they are performing a task. It rates performance across six dimensions to determine an overall workload rating. The six dimensions are as follows: mental demand, physical demand, temporal demand, effort, performance, and frustration level. Dimensions will be weighted and a fatigue index score will be calculated with computer software. The SOFI questionnaire is a comprehensive assessment of a participant's subjective perception of fatigue that explores fatigue across 5 domains rated on a sliding 7 point scale: lack of energy, physical exertion,

physical discomfort, lack of motivation, and sleepiness. Participants will complete these questionnaires after providing mask ventilation with each of the two mask ventilation techniques (MVG and 2VE.)

Objectively, fatigue will be measured by recording the changes in tidal volumes achieved per machine delivered breath temporally over the course of 2 three-minute mask ventilation periods.

EXPLORATORY OBJECTIVES:

Exploratory aim 1: One of our exploratory aims is to compare the efficacy (as described above in primary objectives) of the MVG device versus standard 2VE amongst individuals with smaller hands/weaker grip and individuals with larger hands/stronger grip strength.

Exploratory hypothesis 1: Regardless of hand size and grip strength, all individuals will appreciate an increase in tidal volumes with MVG than with standard 2VE, but individuals with smaller hands/weaker grip will appreciate a greater increase in tidal volumes achieved with the MVG device compared to the 2VE technique than individuals with larger hands/stronger grip.

Exploratory aim 2: Our second exploratory aim is to compare the level of difficulty perceived and fatigue (as described above) appreciated while using the MVG device for mask ventilation compared to the standard 2VE amongst individuals with smaller hands/weaker grip strength and individuals with larger hands/stronger grip strength.

Exploratory Hypothesis 2:

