Regardless of hand size and grip strength, all individuals will appreciate a decrease in difficulty and appreciate lesser fatigue with the MVG device than with standard 2VE, but individuals with smaller hands/weaker grip will appreciate a more significant decrease in difficulty and less fatigue than individuals with larger hands/stronger grip.

3) **Background***

Face mask ventilation (MV) is a basic and essential skill in airway management. It is defined as the procedure of external placement of a mask over patient's face with adequate pressure to form an effective seal over the bridge of the nose, malar eminences, and the mandibular alveolar ridge.[1] In respiratory emergencies, effective MV is essential to ensure adequate patient oxygenation and ventilation until the patient's airway is secured by either a supraglottic airway device or an endotracheal tube.[2] Even though MV is considered a routine procedure, adequate BMV is sometimes challenging even in experienced hands. During in-hospital emergency situations, the initial caregivers at patient's bedside are caregivers with varied duration of experience, which include emergency medicine physicians and/or anesthesiologists. The technique of MV requires understanding facial contours, mask

design, and its effective application.[3] This requires sufficient experience as shown by difficulty in providing effective MV by novices, emergency room technicians, pre-hospital team personnel, nurses and operating room personnel other than anesthesiologists and emergency medicine physicians who perform MV regularly.[3, 4]

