Recruitment and consenting strategy

Recruit a sample of medical students, residents and attendings at the Miller School of Medicine of the University of Miami.

The study will be performed at the Center for Patient Safety (CPS). The CPS is an educational site for residents, medical students and attendings to undergo specialized simulation- based training. As these three groups attend their regularly scheduled training sessions, they will be approached by a member from the research team to assess their willingness to participate after their simulation session in the study. If willing, they will be advised that it will be only this one session and their participation is voluntary and that it is in no way connected to their academic, educational assessment and grades.

We will obtain written consent from all participants. No participant will receive any compensation for their participation. We will maintain documentation of participant flow in accordance with the Consolidate Standards for Reporting Trials Statement. Figure 2 [12]

[figure not shown]

Figure 2. Consolidated Standards of Reporting Trials (CONSORT) diagram of participant enrollment, allocation, and analysis[13].

8) **Risks to Subjects***

There is a minimal risk associated with this study. We propose a prospective cross-over single center cohort study that will include anesthesiology residents and

attendings. The study will be performed at the Center for Patient Safety, University of Miami Miller School of Medicine.

The only descriptors which will be collected include age, gender and years of experience, which will remain secured.

9) Confidentiality

The descriptors mentioned above will be collected on the approved data sheet., with each participant assigned an alphanumeric label. Study data will be accessed only by the PI and the team.

All data forms are going to be stored in the office of the Principal Investigator, Department of Anesthesiology, Jackson Memorial Hospital, [name]. Data transferred to an excel spreadsheet will be stored electronically in a secured encrypted file on the Principal investigator's Computer. The Investigator (or research staff) will record (e.g. write down, abstract) data collected in a manner that does not include any indirect or direct identifiers and the recorded data will not be linked to the individual's identity.

10) Provisions to Protect the Privacy Interests of Subjects

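### Does measuring grip force only after both ventilation periods spoil it as a moderator in the exploratory aims?

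*Combined protocol and SAP*

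**What the plan says.** Section 2, Objectives, gives grip strength, paired with hand size, a directional role in both exploratory hypotheses. For tidal volume, "individuals with smaller hands/weaker grip will appreciate a greater increase in tidal volumes achieved with the MVG device compared to the 2VE technique". For difficulty and fatigue, "individuals with smaller hands/weaker grip will appreciate a more significant decrease in difficulty and less fatigue than individuals with larger hands/stronger grip". The Measurements part of section 6 repeats the purpose ("Hand fatigue and efficacy of MVG compared to 2VE in regards to" hand size and grip strength) but names no model or cut-off.

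The timing is in section 6: "As the final component of the experiment, participants will have their dominant hand measured for hand span, palm circumference, and max grip force produced". Two periods of 30 breaths, about 3 minutes each, come first, with a 5-minute rest between them. After the second period come both questionnaires, two tape measurements and a dynamometer demonstration. The grip score is then the mean of three maximal attempts. No rest is timed before those attempts, and the baseline list (age, gender, years of experience) does not include grip.

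Two other statements bear on the point. The secondary hypothesis says "Hand-fatigue is reduced by using the ventilation grip device compared to the standard 2VE technique in both expert and novice groups". Order is set by a draw, after which "the participant will begin with this technique and then switch to the alternative", so the technique used last differs between participants.

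**The concern.** A moderator is normally read before the exposure whose effect it is meant to explain. Here the reading follows a task that the protocol expects to tire the hand, and to tire it more with one technique than the other. If recovery is incomplete, measured grip is pre-task strength minus some fatigue. For exploratory aim 2 the link looks circular, because fatigue is also the outcome: a participant badly tired by 2VE could show both a weak grip and a large apparent benefit from the MVG, which is the pattern the hypothesis predicts. For exploratory aim 1 the fatigue component would act as noise and hide a real relation. With no pre-task reading, the data could not show afterwards which had happened. The dynamometer test does not depend on technique, so moving it before the draw looks free.

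**Working it through.** The documents give no figure for residual fatigue, so there is nothing of the plan's own to reproduce. What can be checked is which conditions cause harm, and how much.

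**Inputs from the plan.** The draw uses 16 + 16 = 32 slips, 8 and 8 per group, so 16 participants per sequence. At 10 breaths per minute, 30 / 10 = 3 minutes per period.

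**Assumed inputs.** MVG fatigue has SD 1. 2VE fatigue has SD s and a mean higher by d. The within-person correlation is 0.5. Fatigue shifts by p in the second period. Measured grip is g − k × (last-period fatigue), where g is true grip with SD 1, unrelated to benefit. Benefit B is 2VE fatigue minus MVG fatigue.

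**When a false relation arises.** Within the sequence ending on 2VE, the covariance of last-period fatigue with B is s² − 0.5s. Within the other sequence it is 0.5s − 1. The average is (s² − 1)/2. Between sequences, last-period fatigue differs by d and B differs by 2p, which adds d × 2p / 4 = dp/2. So

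cov(grip, B) = −k × [(s² − 1)/2 + dp/2].

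If the variances are equal (s = 1) and there is no period shift (p = 0), this is zero whatever the size of d. A technique difference with randomised order therefore does not create the circular relation.

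**Size.** The correlation is that covariance divided by √(Var grip × Var B), where Var grip = 1 + k²[(1 + s²)/2 + d²/4] and Var B = 1 + s² − s + p². For s = 1.3, d = 1, p = 0.5, k = 0.5:
- covariance = −0.5 × (0.345 + 0.25) = −0.2975
- Var grip = 1 + 0.25 × 1.595 = 1.399
- Var B = 1 + 1.69 − 1.3 + 0.25 = 1.64
- r = −0.2975 / √(1.399 × 1.64) = −0.20

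Simulated rejection rates of a two-sided 5% correlation test, n = 32, no true moderation:

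| Setting | k = 0.1 | k = 0.25 | k = 0.5 | k = 0.5, half of score variance is error |
|---|---|---|---|---|
| d = 1 only | 5.0% | 5.1% | 5.3% | – |
| s = 1.3 only | 5.3% | 6.9% | 11.4% | 7.0% |
| d = 1, p = 0.5 | – | 6.1% | 8.6% | 6.4% |
| s = 1.3, d = 1, p = 0.5 | 5.7% | 9.5% | 19.8% | 10.3% |
| s = 1.5, d = 1, p = 0.5 | – | – | 30.2% | 14.0% |
| s = 1.3, d = 1, p = −0.5 | – | – | 5.6% | – |

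A dash marks a setting for which no figure is given. In the last row the two terms nearly cancel (0.345 − 0.25 = 0.095). A pre-task reading gives 4.9 to 5.1% throughout.

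**How strong k = 0.5 is.** The share of measured-grip variance that is fatigue is (Var grip − 1)/Var grip. With d = 1 it is 0.3125/1.3125 = 24% at s = 1, 0.399/1.399 = 29% at s = 1.3 and 0.469/1.469 = 32% at s = 1.5. That is a lot for a reading taken after questionnaires, tape measurements and a demonstration.

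**Why the last column is the fairer one.** The other columns treat the questionnaire score as the exact cause of lost grip force. Section 2 describes NASA-TLX as a mental-workload scale, and SOFI includes sleepiness and lack of motivation. Much of either score is not hand-force loss.

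**Noise in exploratory aim 1.** If true grip correlates −0.45 with tidal-volume benefit, the observed correlation is −0.45/√(Var grip). At k = 0.5 and s = 1 this is −0.45/√1.25 = −0.40 with d = 0, or −0.45/√1.3125 = −0.39 with d = 1. Simulated power falls from 76% to 75–76% (k = 0.1), 72–73% (k = 0.25) or 62–65% (k = 0.5).

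**Cost of testing grip first.** Suppose three maximal squeezes shift first-period tidal volume by q SDs of the paired difference. The MVG−2VE mean stays balanced, since 16 participants gain q and 16 lose it. But section 7 says "T-paired test model will be used for comparison of the tidal volumes between two groups", with no period term, so the estimated variance rises from 1 to about 1 + q². Power set at 80% becomes 79%, 79%, 77% or 73% for q = 0.1, 0.2, 0.3 or 0.5.

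**The case for a change.** The strongest case for acting is that the facts are not in dispute, the design cannot show afterwards how much fatigue the reading carried, and the change moves an existing step without adding one. Adjusting for sequence in the analysis does not reliably replace it. At k = 0.5 it cuts 19.8% to 11.0% in one setting but raises 5.6% to 11.0% in another. The loss of power in exploratory aim 1 needs only residual fatigue that varies between people.

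All of that stands as description. It does not show that the move is a gain. The squeezes would come before the primary outcome, before the first-period NASA-TLX and SOFI ratings, and before the breath-by-breath change in tidal volume that section 2 uses as the objective fatigue measure. The power figures for testing first cover only the mean tidal volume; the effect on the fatigue outcomes is unpriced, and those outcomes rank above the aims being protected. Nor would an early reading be sure to come from a rested hand, since the recruitment section has staff "assess their willingness to participate after their simulation session in the study". A timed rest before the final grip test avoids these costs and would do no harm. Some recovery is already built in, though: the same two questionnaires fill the 5-minute rest between periods, and the tape measurements and demonstration then follow. No result in the plan depends on adding a timed rest.

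**Conclusion.** The observation is accurate, but it does not call for a change. Grip is read after the task and may carry residual fatigue of unknown size. Every participant performs both techniques first, so a uniform loss would leave rankings and correlations unchanged. A technique difference alone produces no meaningful excess of false positives (5.0 to 5.3%). Excess requires unequal fatigue variance, or a technique difference combined with a period shift. With allowance for score error it is about 6 to 14%, even with fatigue making up roughly a quarter to a third of measured-grip variance. The loss of power is about 1 point if contamination is slight and 11 to 14 points if it is strong. These figures rest on assumed values of k, s, d and p, which the documents neither give nor exclude.

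The exposure is limited to the grip half of two exploratory aims. Hand span, palm circumference and the primary and secondary outcomes are untouched. Keeping maximal effort away from the higher-ranked outcomes is a reasonable choice, and analysts writing up the grip results can simply state when grip was measured.
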